All data will be collected by the primary provider, site principle investigators, or site coordinators. This data will be disassociated with personal identifiers, re-associated with a nondescript study ID, and uploaded into OHSU-sanctioned confidential data management service such as RED Cap, on a daily basis.

We will collect basic demographical information, including age, gender, ethnicity, substance abuse disorder/drug of choice and current use status, and housing status. The primary outcome measured will be SVR at 24 weeks (12 weeks post-treatment). Secondary outcomes include adherence (% pills missed, per fill and total), relapse or ongoing injection drug use at 48 weeks, and re-infection or treatment failure at 48 weeks.

Data storage will be for a period of 5 years or less, unless formal permission requested of the OHSU IRB for extension. Subjects will be consented for indefinite data storage.

Please see uploaded data collection and consent forms.

b. Sharing of Results with Subjects

All personal, clinical information will be shared with subjects in accordance of the standard of care. This includes lab values (done at CLIA certified laboratories Quest and Labcorps), imaging results, and other aspects of routine hepatitis C treatment. Results of secondary measures, including survey data and indepth interviews, will not be shared directly with subjects. Subjects will be able to access the final publication(s) upon request.

c. Data and Specimen Banking

Subjects will be assigned a study ID on paper and data will be entered into an encrypted/password protected excel spreadsheet by the site principle investigator or study coordinator. The study ID will not contain any of the 18 HIPPA identifiers and will be available only to the PIs and IRB approved study collaborators. This document will be maintained, password protected, in the RED Cap repository. At each visit, a subject's study ID will be accessed from the Master List and a de-identified, study ID-linked opaque envelope with data sheets for all 10 visits will be pulled from a secure location. All non-clinical care data will be initially collected on paper by the data collector, provider, or study coordinator and then entered into de-identified data sets in the RED Cap repository by the study coordinator on a weekly basis. The paper copy will be replaced into the opaque envelope and then confirmed by a separate, IRB approved study volunteer. Standard of care clinical data will be entered in the electronic medical record and endpoints pre-specified in this protocol will be transferred to the RED Cap repository by the study coordinator on a weekly basis. When the study is fully enrolled and all participants complete the 48week visit, or are lost to follow up, the paper datasets will be destroyed in medical recycling facilities at each site.

In the retrospective OHSU cohort, all data will be entered immediately into RED Cap and then confirmed by a separate investigator at the OHSU site.

As part of the primary consent document, all participants will legally consent by written signature to storage of non-biological study data in a secure repository for future investigations. No biological specimens of any type will be stored beyond what is needed to complete laboratory tests at the point of care. For instance, blood will be drawn and sent to the clinical laboratory (LabCorp, Quest Diagnostics)

and stored ONLY for the purposes of performing the lab, in concordance with standard practices. In most cases this will not exceed a week and never more than two weeks. No genetic testing will be performed as a part of this study and thus none will be shared. All electronic data will be maintained encrypted in the RED Cap repository. Only the primary investigator, [name], and two coinvestigators, [name] and [name], will have access to these data following study termination. These data will be maintained separate from personal identifiers, and only the PI and coinvestigators will have access to the master spreadsheet linking study ID and personal identifiers. These personal identifiers will not be made available to external researchers at any time, and so no personally identifiable information will be shared with external researchers. [name], co-investigator and primary study contact, will be listed as the repository guardian. If contacted for use of study data for any purpose, he will be responsible for ensuring data are released according to OHSU policy and the IRB approved repository protocol, executing a repository sharing agreement in case data are released for future research, ensuring the security and confidentiality of all stored data, ensuring the security and confidentiality of data during transfer, and tracking acquisitions and releases of data. He will also maintain access to the master spreadsheet linking study ID to personal identifiers, in order to identify data sets for which consent has been withdrawn and ensuring no future use.

After study completion, any future release of data collected will be contingent upon the repository guardian verifying a separate full IRB approval for each specific human subject research activity that uses identifiable repository data. The repository guardian will be personally responsible for verifying that future releases of data are done in concordance with pre-proposed limits and the original consent. Data transport at the time of any potential future IRB approved data sharing will be clarified and approved at the time of data by submission of an updated Repository Sharing Agreement and separate IRB approval. Any updated data requests and Repository Sharing Agreements will be stored alongside study data in the Red Cap repository in a separate file entitled "Repository Sharing Agreements and External Data Requests." This will be maintained and tracked by [name]. External researchers will be required to use the Red Cap repository for all data storage, therefore data transfer will not be necessary and data security ensured.

No data submittal from outside sources is expected.

8. Data Analysis

- 1) For primary endpoint: descriptive analysis and chi-squared test for comparative analysis
- 2) For secondary endpoints:
 - Descriptive analysis
 - Explore bivariate and multivariate associations between psychosocial factors computed through scales (e.g., stigma, social support, quality of life) and (a) treatment readiness at baseline, (b) treatment outcomes [SRV, biological outcomes, etc.] at 12 months, (c) re-infection (or SRV) at 48 months. Demographic controls will include age, education, work status, and relationship status.
 - Conduct constant comparative qualitative analysis of focus group and individual discussions using Atlas.ti software. The domains of analysis will include lived experiences with stigma, discrimination, positive and negative social support systems, and risk management. Emergent themes and domains identified through qualitative analysis will result in a richer understanding of factors that contribute to implementing successful treatment for people who currently use drugs.

In addition to the above, mixed methods data will comprise biological data, psychosocial data collected via questionnaires, and qualitative narrative data from transcribed in-depth interviews.

Using Dedoose software, the research team will work together to systematically analyze the data in the following steps: 1) exploratory within-case analysis; 2) descriptive across-case analysis; 3) analytic within-case analysis; and 4) analytic across-case analysis—each “case” being an individual included in the study.

The overall goal is to draw connections among the domains laid out in the socio-ecological conceptual framework, exploring patterns that indicate how social and institutional experiences may shape vulnerability to HCV and success in treatment outcomes. This type of reflexive analysis is crucial when performing real-world clinical research that takes into account psychosocial factors and social context.

Exploratory within-case analysis involves reading interviews and marking sections with compelling and/or representative stories, quotes, or instructive idioms. Noteworthy aspects of each case are summarized, contributing to the development of a preliminary set of codes. Rather than deciding a priori the taxonomies for sorting individuals, themes and codes emerge from the data itself.

Descriptive Across-Case Analysis involves generating descriptions of key domains articulated in the socio-ecological conceptual framework. This across-case analysis will describe the range within each domain, articulating—for example—the range of participants’ experiences interacting with medical institutions, trust in medication, experiences of stigma related to HCV or drug use, subject social network’s views of medical treatment, as well as institutional elements of receiving care at community clinic settings with multiple social services.

For the analytic within-case analysis, the team will develop and test explanations of how the institutional and social contexts of people’s lives shape their treatment outcomes. This includes adherence to treatment, SVR, and vulnerability to HCV reinfection. This involves pooling interview, biological and psychosocial data to describe frequencies and relationships between key domains and outcomes. This analytic within-case analysis will correct for any theoretical oversights in the conceptual framework and may generate new analytic codes.

Analytic across-case analysis entails comparative analysis, distinguishing between groups of people who exhibit different behavioral patterns. This allows the investigators to go beyond simple assertions about majority and minority patterns and to make analytic—as opposed to descriptive—statements about how certain values or behaviors relate to broader psychosocial and institutional factors.

Power/Sample Size:

Based upon a sample size of n=50 subjects in the combined safety net/needle exchange clinics and 50 subjects in the retrospective comparator group, this study has 80% power to detect a 20% difference between groups; this calculation is based on the assumption that the retrospective comparator group will have and SVR12 rate of 95% (taking into account treatment discontinuation and relapse rates, i.e. intention to treat analysis) compared to SVR12 rate of 70% in the safety net clinic patients.

In the intervention group (safety net clinics) a total of 50 subjects will be enrolled to allow for a 10% attrition and loss to follow up.

9. Privacy, Confidentiality, and Data Security

All data will be collected and entered in a private, clinical care environment, behind closed doors. All study collaborators with access to personal data, de-identified or not, will be required to undergo full OHSU IRB training.

At Old Town Clinic, subjects will be recruited as described in Section 5e. There will be limited risk of a privacy violation with this method. The consent process will be performed during the course of a clinical visit, in an exam room, one-on-one with the site coordinator.

At Outside In, subjects will be recruited as described in Section 5e. There will be limited risk of a privacy violation with this method. The consent process will be performed after a clinical visit in a private office in the syringe exchange, one-on-one with the site coordinator.

At all sites, laboratory and/or imaging tests, clinical visits, dispensation of medications, and communication of test results will be performed in concordance with HIPPA appropriate clinical care. All surveys and qualitative data will be collected in a private space, such as an exam room or meeting room behind closed door.

For more details, please see section 7c above.

10. Provisions to Monitor the Data to Ensure the Safety of Subjects

See DSMP document, attached.

9. Risks and Benefits a. Risks to Subjects

- Surveys and Questionnaires. Some of the questions in the questionnaires or interviews have the potential to be re-traumatizing. All study personnel have training in trauma informed care and know how to minimize this risk. Subjects have the right to refuse to answer any questions.
- Lab Tests and Images. There is minimal risk of discomfort associated with lab draws.
- Treatment. About 1/100 people experience a temporary increase in their serum transaminase, ALT, to about 5 times the upper limit of normal. This typically resolves after completion of treatment. In previous studies, about 1/10 patients experienced headaches and fatigue during treatment. However, this is about equivalent to, or only slightly higher than, placebo in most studies. In one study, patients on Zepatier™ were slightly more likely to have nausea than patients on the placebo. Zepatier™ can interact with some other medications, these will be screened for by study pharmacists and clinicians prior to drug initiation.¹⁰

b. Potential Benefits to Subjects

Zepatier™, and other direct acting antiviral agents targeting hepatitis C, are extraordinarily effective at eradicating the disease, between 92 and 97%¹⁰. The morbidity of hepatitis C is described well above. Patients with lower fibrosis scores are being denied access to treatment by insurance companies in this and other states due to cost concerns, despite this being contrary

to national guidelines. Patients are also frequently denied for having a substance abuse disorder, even though the majority of new infections in the United States occur in this population. As such, we know very little about the treatment of hepatitis C in active or recent PWIJs.

Subjects who participate in this study will have free access to a highly effective, FDA approved treatment for hepatitis that will likely cure their disease. They will also have access to intensive, wrap around services they would not likely enjoy at a referral center where they would typically get treated. The ancillary data collected in surveys and interviews may help individualize therapy options, including prescribing frequency, etc., and will contribute to the body of knowledge to help better care for their community.

10. Drugs or Devices (delete if not applicable)

Open label drug supplies will be required by Merck.

Our institution's pharmacy will require packed and labeled medication containers in English.

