Project Title:

Hepatitis C Treatment in PWIDs: MAT or Syringe Exchange Assisted-therapy vs Standard of Care

NCT Number:

NCT03093415

Last Review/Edits:

January 20, 2019

Protocol 1. Protocol Title

Hepatitis C Treatment in PWIDs: MAT or Syringe Exchange Assisted-therapy vs Standard of Care

IRB 16357

2. Objectives/Hypothesis

Hypothesis: Treatment adherence and hepatitis C (HCV) infection cure rates using a simple 1-pill a day regimen of a direct anti-viral agent (DAA) in two unique care delivery models for marginalized persons with HCV infection, Outside In needle exchange program serving people who inject drugs (PWID) and Old Town Clinic, an integrated multi-disciplinary primary care clinic serving homeless and low income adults, will be similar to HCV patients treated in a traditional Hepatology Clinic at an Academic Health Center

Purpose: Determine if two unique safety net clinics (intervention group) with comprehensive behavioral health, pharmacy and medical services will improve HCV therapy adherence and reduce re-infection rates such that overall cure rates will be maintained and be similar to cure rates seen over the same time period in a traditional hepatology clinic setting (comparison group). The expectation is that these safety net clinics with comprehensive healthcare services should normalize the chaotic lifestyles of the patients that typically utilize safety net clinics.

Goal: If this study can demonstrate that such well-established comprehensive multidisciplinary safety net clinics that see an extremely marginalized population that are typically excluded from access to HCV therapies can achieve similar HCV treatment responses as seen in traditional clinics, the use of such sites as HCV treatment centers can be utilized on a national scale.

AIMS:

1. Identify clients/subjects in each care setting with genotype 1 or 4 HCV infection ≥ 18 years of age that wish to be treated.
 - a. Outside In Injection Drug Users Health Services (n=25)
 - b. Old Town Clinic (n=25)
 - c. Retrospective cohort of subjects at Oregon Health & Science University Hepatology Clinic (n=50)
2. Prior to treatment each client/subject is administered a questionnaire assessing motivation, readiness for treatment
3. Assess adherence to treatment regimen, laboratory testing, discontinuation rates, cure rates, and reinfection rates 1 year post treatment

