4. Compare results across the three care delivery sites and identify any patient-related variables that impact treatment success

3. Background

Since the introduction of the first DAAs to treat HCV about 2 years ago, there are compelling reasons for expanding access to treatment for all HCV patients including their safety and cost-effectiveness.¹ However, certain HCV populations such as the homeless and people who inject drugs (PWID) have a high prevalence of chronic HCV infection. At the same time these populations have significant barriers to accessing care and have low rates of treatment initiation for their HCV infection. The impact of highly potent and well-tolerated interferon-free HCV treatment regimens will remain negligible as long as access to therapy cannot be expanded to the most affected risk groups.

One strategy that addresses several barriers is co-localization or integrated care of HCV screening, evaluation, and treatment with other medical or social services. Co-localization has already been applied to settings with a high prevalence of HCV infection (e.g., correctional facilities and programs providing needle exchange, substance abuse treatment, and methadone maintenance) but is not uniformly available.

One of the major obstacles to HCV care in the homeless and PWID is the lack of treatment settings that are suitably adapted for the needs of this vulnerable population. Nevertheless, HCV treatment has been delivered successfully to PWID through various multidisciplinary models such as community-based clinics, substance abuse treatment clinics, and specialized hospital-based clinics. Models may be integrated in primary care--all under one roof in either addiction care units or general practitioner-based models--or can occur in secondary or tertiary care settings. Additional innovative models include directly observed therapy and peer-based models.
2,3,4

This current study uses a mixed care model approach where two unique safety net sites, one serving the homeless and the low income and the other, active injection drug users who utilize a needle exchange program, working in concert with a traditional gastroenterology/hepatology clinic to identify and treat HCV patients within their own care environment. A unique feature of this study is maintaining a real world setting for HCV treatment to occur. Allowing therapy to be given in an environment that is familiar and supportive should foster adherence and high rates of treatment success.

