The results of this study will give insight into the feasibility of using safety net medical sites such as needle exchange programs and community health centers serving low income or homeless populations to safely and effectively treat this vulnerable population that is disproportionately affected by HCV infection. Furthermore, feedback from clients/patients using validated questionnaires could identify modifiable barriers to treatment success. Findings from this study could help expand the HCV treatment capacity beyond subspecialty practice and even the traditional primary care clinic.

4. Study Design

Study Objectives

Primary Objective: Determine if the clinical effectiveness of Zepatier in treating patients with HCV infection and mild fibrosis in two safety net sites, which offer comprehensive services to normalize the chaotic lifestyles of people who inject drugs and the homeless, is similar to what is expected in a tertiary hepatology clinic that cares for a more traditional patient population.

Secondary Objective: Identify client/patient factors that impact HCV treatment success in this population

Study Endpoints

Primary Endpoint

- Sustained virologic response rates measured at 12 weeks post treatment (SVR12)-Intention to Treat analysis (taking into account treatment discontinuation and failure rates)
- Persistently HCV infection free after 48 weeks of treatment cessation (SVR48)

Secondary Endpoints

- Adherence determined by client/subject self-reported medication adherence measured by percentage of pills taken on a monthly basis, as well as compliance with laboratory testing

- Treatment discontinuation rates including loss to follow up
- Percent of genotype 1a patients with baseline NS5A resistance

Relapse with substance use disorder in Old Town Clinic setting

Exploratory analysis of potential client/subject factors impacting readiness for treatment, non-adherence, or reinfection based on questionnaires administered at baseline and at 48 weeks post treatment

Study Design

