This will be a prospective study at the two safety net clinic sites where 25 non-cirrhotic subjects at each site will receive HCV treatment with Zepatier. Patients will be followed by a care team comprised of a medical provider and pharmacist at each care site within their own medical home environment. Subjects will be monitored for treatment and lab adherence. Overall SVR 12 will be assessed for this study group. This SVR12 rate will be compared to the SVR12 rate of a retrospective cohort of 50 consecutive non-cirrhotic HCV patients treated in the Hepatology Clinic at Oregon Health and Science (OHSU) starting in 2015. A prospective cohort will not be necessary at OHSU, since SVR12 rates have been consistently within the range of what has been reported in the literature.

Study Definitions

Treatment failure -

- Primary treatment failure: detectable HCV RNA at week 12 post-treatment.
- Secondary treatment failure: despite achieving SVR12, detectable HCV RNA at 48-week follow-up posttreatment. This would suggest re-infection, if there is evidence of re-exposure to virus. In addition, repeat genotyping will be performed in order to determine if the genotype has changed from baseline. If so, this would also suggest re-infection.

Treatment discontinuation- therapy interrupted by either the subject due to compliance issues/side effects or by medical provider due to safety issues.

Reinfection- achieved SVR12, but at 48 weeks after completing HCV therapy HCV RNA is detected. If there is evidence of re-exposure to HCV infection and/or repeat genotyping demonstrates a different genotype from baseline genotype prior to starting HCV therapy.

Treatment Regimen Compliance -

- Medication Compliance- percentage of pills taken during 12-week therapy. Pill count is assessed at every clinic visit.
- Laboratory Compliance- percentage of completed scheduled lab draws
- Clinic Visit Compliance- percentage of attended scheduled clinic visits

5. Study Population

a. Number of Subjects

A total of 50 *retrospective* subjects will be enrolled at OHSU. Two separate prospective cohorts of 25 patients each will be enrolled at Old Town Clinic and Outside In, prospectively.

b. Inclusion and Exclusion Criteria

Prospective Study Cohort

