- Screening, treatment interventions, and follow up are outlined below. All of the following represent standard of care interventions, with the exception of survey data collection and in-depth qualitative interviews. These interviews serve the purpose of better understanding potential barriers to successful treatment and to identify potential mitigating innovations in the care of this complicated and neglected population.

Treatment Scheme

Baseline Testing (already performed as a part of standard of care for a patient with HCV infection)

- CBC with differential, Complete Metabolic Profile, GFR, INR, HCV genotyping with NS5A resistance testing for genotype 1a, HCV RNA, HIV, pregnancy test in female of childbearing age
- APRI score or Fibrosure or Fibroscan to determine fibrosis stage. APRI score is defined as AST level in IU/L over 40 IU/L (upper limit of normal value) divided by platelet count in $10^9/L$ multiplied by 100 or.

Screening Visit

- Consent process including discussion of the consent form
- History and physical to exclude signs and symptoms of cirrhosis
- Inclusion and exclusion criteria assessed
- NS5A resistance testing for genotype 1a subjects (subjects excluded if baseline resistance present)
- Assess subject's readiness for treatment: Subjects must have established care as a primary care patient at Outside In or Old Town Clinic. They must express a desire to be treated and to adhere to all laboratory monitoring and visit requirements.
- Screen failure subjects will be linked to appropriate care within the study site or at OHSU hepatology for further management

Visit 1

- Clinic Visit
- Once enrolled, completion of validated questionnaires (see Appendix that includes additional references) that assess the subject's understanding of health, current health status, addiction and severity of addiction, social support, and degree of stigma. These assessments have been described in hepatitis C infected population.^{6,7,8}

Visit 2

- Clinic visit
- Verify the following studies/assessments are complete including CBC; INR, complete metabolic profile; GFR; genotype 1a, 1b, or 4 HCV RNA; no baseline RAVs for genotype 1a subjects
- Verify Readiness for treatment

- Verify questionnaires completed
- Pregnancy counseling

Visit 3 (Initiation of HCV treatment)

- Clinic visit
- Check in post-survey on subject well-being
- Pharmacy dispenses 2 weeks, or less if indicated* of HCV medication

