*Given the complexity of this population, the study pharmacist and clinicians will determine the most appropriate dispense frequency and method depending on the subjects' needs.

Visit 4 (week 2 of HCV treatment)

- Clinic Visit
- Compliance assessment
- Pharmacy dispenses another 2 weeks, or less if indicated, of HCV medication

Visit 5 (week 4 of HCV treatment)

- Clinic Visit
- Compliance assessment
- HCV RNA (if detectable, repeat HCV RNA in 6 weeks)
- Pharmacy dispenses 2 weeks, or less, if indicated, of HCV medication

Visit 6 (week 6 of HCV treatment)

- Clinic Visit
- Compliance assessment
- Recheck HCV RNA in those subjects who had detectable HCV RNA at week 4. If on repeat testing at week 6, viral load has increased by 10 fold $>1 \log_{10}$ IU/mL discontinue therapy. **Visit 7 (week 8 of HCV treatment)**

of HCV treatment)

- Clinic Visit
- Compliance assessment
- Check CMP. If liver enzymes >10 fold discontinue therapy

VISIT 8 (week 12 of HCV therapy) - End of Treatment

- Clinic Visit
- Compliance assessment

VISIT 9 (week 24) - 12 weeks after treatment completed

- Clinic visit
- HCV RNA to assess for SVR12, repeat genotype to clarify re-infection vs failure if +

VISIT 10 (week 60) - 48 weeks after treatment completed

- Clinic visit
- HCV RNA to assess for SVR48, repeat genotype to clarify re-infection vs failure if +
- Re-administer questionnaires

TOTAL DURATION - about 18 months

Quantitative Survey Data.

The following surveys will be performed and have been submitted for IRB approval:

- Chronic Illness Anticipated Stigma Scale (CIASS)
- MOS Social Support Survey
- SF-36 “Health and Well-Being” Survey

In addition, in-depth qualitative interviews will be performed Interviews will cover salient issues in participants’ lives at the community, organizational, household levels, as well as relationships (friends, family and sexual partners) perceived to influence study participation, treatment acceptability and adherence; risk taking behavior; and treatment preferences. By emphasizing the social and physical context of participant’s lives and their understandings of health, interviews are intended to provide insight into the ways in which these contexts shape treatment adherence and possible reinfection. The following constructs are constructs and sample themes that will guide in-depth interviews.

Level	Factors	Topics/Theme

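### The plan implies a 48-week comparison (SVR48, re-infection) with OHSU, but specifies 48-week testing only for the prospective subjects and gives no collection or scoring rule for the OHSU half of the sample

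*Combined protocol and SAP*

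**What the plan says.** **Text that implies a 48-week comparison with OHSU**

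- Section 2, Purpose: the safety-net clinics are expected to reduce re-infection so that overall cure rates stay similar to those of the hepatology clinic over the same period.
- Section 2, Aim 3 covers "discontinuation rates, cure rates, and reinfection rates 1 year post treatment", with no restriction to the prospective sites. Aim 4 follows directly: "Compare results across the three care delivery sites". Aim 1 names the retrospective OHSU cohort as the third site.
- Section 4, Primary Endpoint, second bullet: "Persistently HCV infection free after 48 weeks of treatment cessation (SVR48").
- Section 8: "For primary endpoint: descriptive analysis and chi-squared test for comparative analysis". SVR48 is not excluded.

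**How the 48-week outcomes are obtained**

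- Section 4, Study Definitions: re-infection means the subject "achieved SVR12, but at 48 weeks after completing HCV therapy HCV RNA is detected", together with evidence of re-exposure and/or a changed genotype.
- Section 6, Visit 10 (week 60): "HCV RNA to assess for SVR48, repeat genotype to clarify re-infection vs failure if" positive. The Screening Visit of the same scheme requires established primary care at Outside In or Old Town Clinic, so the scheme is written for the prospective subjects.
- Sections 5b and 5e: OHSU subjects are selected from the electronic medical record.

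**Text that points to SVR12 only**

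- Section 4, Study Design, spells out the OHSU comparison for SVR12. It also justifies having no prospective OHSU cohort by SVR12 rates.
- Section 7a names SVR 12 weeks post-treatment as the primary outcome and puts 48-week re-infection or failure among the secondary outcomes.
- Section 8, Power/Sample Size, covers SVR12 only.

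**The concern.** A 48-week outcome can be scored only in someone tested at about 48 weeks. One group has a scheduled visit for this. The other has whatever its charts happen to contain. The protocol does not require a late RNA for OHSU selection, define an acceptable window, say where genotype or re-exposure information comes from, or say how an untested OHSU patient counts.

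A chi-squared test on these data would compare scheduled testing with incidental testing. If untested patients count as failures, the OHSU rate falls with every missing test, whatever the true cure rate. If they are dropped, the OHSU group shrinks to those who were tested, for reasons the protocol does not describe. Either way, a statement about durable cure or re-infection relative to hepatology care could reflect testing practice rather than outcome. Such a statement is part of the study's stated Purpose.

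**Working it through.** **Step 1. The plan's own figure.** The only power statement is for SVR12: 80% power for a 20-point difference with 50 per group. Alpha is not stated, so I assume two-sided 0.05.

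Power = Φ{[|p1 − p2|·√n − 1.96·√(2·p̄·(1 − p̄))] / √(p1(1 − p1) + p2(1 − p2))}

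- 95% vs 75%, n = 50: (0.20 × 7.071 − 1.96 × √0.255) / √0.235 = (1.414 − 0.990) / 0.485 = 0.876, so power is 80.9%. The stated figure reproduces.
- The rates printed in the same sentence, 95% vs 70%, are 25 points apart and give about 92%. That inconsistency is a separate matter, and this point does not depend on it.

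No power or sample size is given for SVR48 or re-infection.

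**Step 2. Share of the sample affected.** OHSU 50, prospective 25 + 25 = 50. So 50/100 = 50% of subjects have no scheduled 48-week RNA.

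**Step 3. Untested counted as failure (illustration).** Let f be the fraction of OHSU charts with a 48-week RNA. The documents do not give f, so it is varied. Assume 95% of those tested are negative, borrowing the SVR12 planning rate. Then:

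OHSU SVR48 = round(50 × f × 0.95) / 50

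Compare this by uncorrected chi-squared with an assumed safety-net SVR48 of 40/50 (80%, not in the documents) or 35/50 (70%, the SVR12 planning rate).

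| f | OHSU negative | OHSU SVR48 | p vs 40/50 | p vs 35/50 |
|---|---|---|---|---|
| 0.1 | 5/50 | 10% | 2 × 10⁻¹² | 9 × 10⁻¹⁰ |
| 0.3 | 14/50 | 28% | 2 × 10⁻⁷ | 3 × 10⁻⁵ |
| 0.5 | 24/50 | 48% | 0.0009 | 0.025 |
| 0.8 | 38/50 | 76% | 0.63 | 0.50 |
| 1.0 | 48/50 | 96% | 0.014 | 0.0005 |

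Example, f = 0.5 vs 40/50: χ² = 100 × (24 × 10 − 26 × 40)² / (50 × 50 × 64 × 36) = 11.1, p = 0.0009.

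The assumed cure rate among those tested is 95% in every row. Only the number tested changes. The result runs from significantly favouring the safety-net sites (f up to 0.5), through no difference (0.8), to significantly favouring OHSU (1.0). Before rounding, the OHSU rate is understated by 95 × (1 − f) points: 19 points at f = 0.8 and under 5 at f = 0.95.

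**Step 4. Untested dropped (illustration).** The formula of Step 1 with unequal groups, against 50 safety-net subjects:

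| OHSU charts with RNA | Power, 95% vs 75% | Power, 95% vs 70% |
|---|---|---|
| 50 | 81% | 92% |
| 40 | 75% | 88% |
| 25 | 58% | 75% |
| 10 | 19% | 31% |

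With 10 tested and 9 negative, the exact (Clopper-Pearson) 95% interval is 55% to 99.7%. These figures show lost precision only. Any bias from who was tested comes on top and cannot be sized from the documents.

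**The case against.** The strongest reply is that this is a gap in specification and not an invalid analysis. Three parts of it stand.

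1. A reader might infer that OHSU patients have no 48-week RNA and so cannot be scored at all. The documents do not say that. Section 6 introduces the treatment scheme with "All of the following represent standard of care interventions, with the exception of survey data collection and in-depth qualitative interviews", which takes in the Visit 10 RNA. A test regarded as standard of care may well be in some hepatology charts. Availability at OHSU is unspecified, not ruled out.

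2. A reader might infer that the plan commits to a three-site chi-squared test at 48 weeks. No sentence says so in terms. Aim 4 refers to results in general, and the Section 8 line names neither SVR48 nor OHSU. Where the OHSU comparison is spelled out or powered, it is SVR12. Against this, the Purpose, Aims 3 and 4, and the listing of SVR48 under Primary Endpoint point the other way, so the passages need reconciling.

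3. A reader might infer from the low-f rows that OHSU would certainly look worse. Direction and p-value depend on f and on the assumed safety-net rate, as Step 3 shows. Missing = failure is not the written rule for SVR48 either: the intention-to-treat wording is attached to the SVR12 bullet, and no rule is given for SVR48.

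What does not stand is that the gap is harmless. If some charts hold the test and some do not, testing still differs between the groups, and neither way of handling the untested removes that unless nearly all OHSU charts hold the test.

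**Conclusion.** The concern holds as a matter of unequal and unspecified ascertainment. The aims, the endpoint list and the chi-squared line together imply a 48-week comparison with OHSU. The protocol provides for 48-week RNA and repeat genotype only in the prospective subjects, and is silent on collection and scoring for the other 50 of 100.

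The size of any distortion cannot be fixed from the documents. Under the stated assumptions (95% negative among those tested, untested = failure), OHSU SVR48 would read about 10%, 28%, 48% or 76% with 10%, 30%, 50% or 80% of charts holding the test. The SVR12 comparison is not affected. The point should be settled before analysis, but it does not undermine the main comparison.

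**What to change.** - In Aims 3 and 4 and in Section 8, state that the chi-squared comparison with OHSU is for SVR12 only. This agrees with Study Design in Section 4, with Section 7a and with the power statement. Reconcile the Purpose and the Primary Endpoint list with it.
- Report SVR48 and re-infection for the 50 prospective subjects, overall and by site (25 each), as proportions with exact 95% confidence intervals.
- List any OHSU 48-week RNA descriptively, with the number tested out of 50.
- Make no formal OHSU comparison at 48 weeks unless a testing window and a missing-data rule are set in advance and nearly all OHSU charts hold the test.

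**Cost.** Wording only, with no added subjects, visits or tests. The sponsor gives up a formal 48-week comparison with hepatology care, and so any comparative claim on durable cure or re-infection, unless the last condition is met.
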